The aim of this research is to create guidance for VA clinicians who prescribe prostheses to veterans with a lower limb amputation who frequently carry infants, toddlers or other loads. To achieve this aim, we will conduct a human subject experiment with help of twenty individuals with below-knee amputations. Study participants will walk on a treadmill with no added load and four added load conditions using a weighted pack (13.6 kg or ~30 lbs) to simulate an infant, toddler, or other load. The four conditions include the pack strapped to their front, their back, and carried with their arms on the intact limb side and the prosthetic limb side. Each participant will wear a usual prosthetic foot, this same foot with a heel-stiffening wedge, the same prosthetic foot but one category stiffness higher, a new-to-market dual keel prosthetic foot intended for load carrying situations, and a powered ankle foot prosthesis. We will analyze the results of this experiment to determine which prosthetic foot (if any) and which load carrying condition (if any) is most advantageous.

List of Abbreviations

AE – adverse event
ANOVA – analysis of variance
ASIS - anterior superior iliac spine
CCTV - closed circuit television
CO - Colorado
CRQ – continuing review questionnaire
d – Cohen's *d* statistic
EMG – electromyography
GAS - medial gastrocnemius
GMAS - gluteus maximus
GMED - gluteus medius
GRF – ground reaction force
H – hypothesis
HAM - biceps femoris long head
HIPAA – health insurance portability and accountability act
IRB – institutional review board
ISO - Information Security Officer
Kg - kilograms
Lbs - pounds
M - Million
MA – Massachusetts
MD – Maryland
MIRB – Minneapolis Institutional Review Board
N - number of individuals
PHI – personal health identifiers
PI – principal investigator
PO – privacy officer
RF - rectus femoris
ROP – report of other problem
SA – specific aim
SAE – serious adverse event
SOL – soleus
SSWS - self-selected walking speed
TA - tibialis anterior
UW – University of Washington
VA – Veterans Affairs
VAPSHCS – Veterans Affairs Puget Sound Health Care System
VAS - vastus medialis
WA - Washington

Contents

Protocol Title: Load Carriage by Individuals with Lower Limb Amputation.....	5
1.0 Study Personnel.....	5
2.0 Introduction.....	5
3.0 Objectives.....	7
4.0 Resources and Personnel.....	8
5.0 Study Procedures.....	8
5.1 Study Design.....	8
5.2 Recruitment Methods.....	9
5.3 Informed Consent Procedures.....	12

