3.0 Objectives

The purpose of this research is to provide prosthesis prescription guidance for VA clinicians whose patients carry infants, toddlers, and other loads.

The specific aim of this research is to identify the study prosthetic foot that minimizes biomechanical gait deviations when compared to the standard-of-care for veterans with lower limb amputation who carry infants, toddlers, or other loads.

We will conduct a human subject experiment with unilateral transtibial amputees (n=40). Each participant will walk on an instrumented treadmill with no added load and four added load conditions of 13.6 kg: anterior, posterior, intact-side carry, and prosthetic-side carry. Using a

within-subject experimental design with block randomization, each participant will wear: a standard-of-care prosthetic foot, this same prosthetic foot with a heel-stiffening wedge, this same prosthetic foot but one category stiffer, a dual keel prosthetic foot intended for load carriage applications, and a powered ankle-foot purported to adapt to changing loads.

In general, we hypothesize that one of these prosthetic feet will minimize biomechanical deviations for (1) no added load, (2) anterior added load, (3) posterior added load, (4) intact-side carry load, and (5) prosthetic-side carry load.

Our specific hypotheses for each load condition are:

H1 a study prosthesis exists that maximizes the vertical GRF impulse (a measure of body support),

H2 a study prosthesis exists that maximizes the anterior GRF impulse (a measure of body forward propulsion),

H3 a study prosthesis exists that minimizes the peak-to-peak range of sagittal plane whole-body angular momentum (a measure of balance control primarily for anterior and posterior added load conditions),

H4 a study prosthesis exists that minimizes the peak-to-peak range of frontal plane whole-body angular momentum (a measure of balance control primarily for intact-side and prosthetic-side added load conditions), and

H5 a study prosthesis exists that minimizes the mechanical energy expenditure (allow for more efficient locomotion).

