5.6 Data Analysis

Kinematic and kinetic data from the experiment will be processed in Visual 3D (C-Motion Inc., Germantown, MD) and aggregated using custom project specific software (Matlab; Mathworks, Natick, MA). To determine changes in walking performance, we will calculate biomechanical quantities related to body support, forward propulsion and balance control including: the vertical ground reaction force (GRF) impulse, the anterior GRF impulse, and the peak-to-peak range of the frontal and sagittal whole-body angular momentum. We will also calculate mechanical energy expenditure (i.e., the sum of the joint mechanical work of each leg). The GRF and joint work metrics will be normalized by body weight and added load while whole-body angular momentum will be normalized by body weight and added load, walking speed and leg length.

Linear mixed-effects regressions will be used to detect differences in the biomechanical quantities (dependent variables) between study prostheses (independent variables) for each load condition separately (anterior, posterior, intact-side carry, and prosthetic-side carry) following an assessment of normality. This method allows inclusion of subjects who do not complete all study procedures (repeated measures analysis of variance (ANOVA) models do not). These analyses will test for differences between the study prostheses across the four different load carriage conditions with random effects for subject and subject by study prosthesis interaction. If the data is not normally distributed, we will consult with our biostatistician on an appropriate transform. An omnibus test for significance will be generated using a likelihood ratio test with an alpha level of 0.05. Individual pair-wise differences will be assessed using simultaneous inference and associated 95% confidence intervals. All statistical analyses will be performed by study staff using existing VA enterprise software (SPSS Statistics v22; IBM, Inc.). Exact p-values will be reported for each test.

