The satisfaction data from the experiment will be aggregated using project specific software (Matlab; Mathworks, Natick, MA). We hypothesize that there exists a study prosthesis that maximizes satisfaction across the different load conditions. The statistical analyses to test this secondary hypothesis will require a two-factor (prosthesis, load condition) Friedman analysis of variance (ANOVA). This analysis will test for differences between the four different study prostheses across the four different load conditions. The experiment-wise significance will be set a priori at an alpha level of $p<0.05$ and a Bonferroni adjustment will be applied for multiple comparisons. All statistical analyses will be performed using existing VA enterprise software (SPSS Statistics v22; IBM, Inc.). Exact p-values will be reported for each test.

Surface EMG data from the walking trials will be processed with existing custom algorithms in Matlab (Mathworks, Inc.). The collected data will be high-pass filtered (bidirectional Butterworth, 4th order, 50 Hz cutoff frequency), demeaned, and rectified, and then further smoothed using a Version 2.5; 5/14/2021 VA Puget Sound IRB Protocol Template – Version: 12/2015 Page **15** of **20**

moving root-mean-square (RMS) window of 80-ms. Subject average RMS profiles for each muscle at each condition will be normalized to the average peak RMS value of the same muscle for each stiffness setting while walking on the 0° condition. The kinematic and kinetic data will be filtered with a 4th-order Butterworth filter with cut-off frequencies of 6 Hz and 20 Hz, respectively, using Visual3D (C-Motion, Inc.). This data will be used to support the biomechanical observations.

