## Statistical Analysis Plan

Outcome metrics: vertical GRF impulse, anterior GRF impulse, peak-to-peak range of sagittal plane whole body angular momentum (WBAM), and peak-to-peak range of frontal plane WBAM.

Linear mixed effects regression was used to assess differences in biomechanical outcomes (the dependent variable) by foot type for each load by combining all loading conditions in a single model and using a foot type by load condition interaction to estimate means and mean differences in outcomes by foot for each load separately. This model assumes a common variance in outcomes across load and foot. Thus, standard errors for the means will be similar across load and foot. Subject and foot type within subject were considered random effects. Several random effects structures were considered (from subject ID intercept only to a full subject by foot interaction model) with the best model chosen based on likelihood ratio tests. Hypothesis testing for the overall association between outcome and foot type were carried out using conditional F-tests for each load type. For comparison, the Benjamini Hochberg (BH) adjustment was also applied to the F-tests for each model across the 5 load conditions to maintain a false discovery rate of 5%. Hypothesis testing for pairwise differences across feet was carried out using Tukey's method to account for the inflation of the Type 1 error due to assessment of 10 pairwise differences for each load. Analyses were carried out using R 4.2.3 (R Foundation for Statistical Computing, Vienna, Austria) and packages tidyverse, lme4, emmeans and lmerTest.

Outcome metrics: positive net ankle joint work.

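### The protocol summary promises to find the best load-carrying condition, but the plan contains no load contrast, no foot-by-load test and no subject-by-load random effect

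*Protocol*

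**What the plan says.** The protocol summary states that results will be analysed to find the best foot and also "which load carrying condition (if any) is most advantageous". The formal text is narrower. Protocol 3.0: "The specific aim of this research is to identify the study prosthetic foot that minimizes biomechanical gait deviations when compared to the standard-of-care". The hypotheses are introduced with "Our specific hypotheses for each load condition are", and each of H1 to H5 posits a best prosthesis; none ranks loads. Protocol 5.6 plans regressions to detect differences "between study prostheses (independent variables) for each load condition separately", with random effects for subject and for subject by prosthesis.

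The SAP pools all loads in one model per outcome, "using a foot type by load condition interaction to estimate means and mean differences in outcomes by foot for each load separately". Its tests are an F-test of foot within each load, with a Benjamini-Hochberg adjustment across loads for comparison, and Tukey comparisons among feet, 10 per load. On random effects it says: "Subject and foot type within subject were considered random effects". For the ground reaction force and angular momentum outcomes, the structures considered run from a subject intercept up to subject-by-foot. The ankle work model names participant and foot within participant.

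The only analysis that names load as a factor is the secondary two-factor Friedman test of satisfaction in Protocol 5.6. Its stated target is differences between prostheses, and the SAP text does not carry it forward.

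**The concern.** The summary makes a claim about loads that no planned test supports. The rationale also depends on load. Protocol 2.0 argues that a stiffer foot helps under load but loses that benefit without load, and that the dual keel stiffens as load is added. Protocol 5.1 names knowledge of device function under varying loads as the anticipated benefit. Those are foot-by-load statements. Without an interaction test, a reader would have to compare which of five F-tests reach significance, and a difference in significance is not a test of a difference.

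The obvious remedy is to take load contrasts from the fitted model. That has its own problem: without a subject-by-load term, load contrasts averaged over feet are judged against the wrong error. The same omission affects the planned foot contrasts in the opposite direction, at a cost in power.

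**Working it through.** **Step 1. What the plan's own figures cover.** The SAP's 10 comparisons per load equal C(5,2), the pairs of five feet, so all are foot against foot. The power figures in Protocol 5.6 reproduce with a two-sided paired t-test, n=20, alpha 0.05 and SD of the difference = SD × √2 (zero within-subject correlation, an assumption):

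| Case | Difference / SD | Stated power | Recomputed |
|---|---|---|---|
| H1 posterior | 27.0 / 18.3 | 99% | 99.3% |
| H1 anterior | 16.1 / 16.0 | 85% | 85.5% |
| H2 posterior | 1.8 / 1.3 | 98% | 98.6% |
| H2 anterior | 4.1 / 2.4 | 99% | 99.9% |

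All four are differences between two prostheses. No figure concerns a load difference or an interaction, so the power of those tests cannot be computed from the documents.

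**Step 2. Inputs for the random-effects check.** Five feet and five loads (SAP), n=20 (protocol summary and power analysis). Assumed, because the documents give no variance components: residual variance E = 0.5, subject-by-foot variance F = 0.5, and subject-by-load variance L = 0.10, 0.25 or 0.50. So L is 10%, 25% or 50% of F + E = 1.0, or 20%, 50% or 100% of the residual alone.

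**Step 3. Load contrast averaged over feet.**
- Mean square for subject-by-load (19 × 4 = 76 df) has expectation E + 5L; the remaining residual (19 × 16 = 304 df) has expectation E.
- Without the term, the model pools them: [76(E + 5L) + 304E] / 380 = E + L.
- True variance of the contrast: 2(E + 5L)/(5n). Variance the model reports: 2(E + L)/(5n).
- Ratio R = (E + 5L)/(E + L). The factor n cancels.
- Error of one contrast is about 2[1 − Φ(1.96/√R)]. For six Tukey contrasts among four loads, it is the chance that the studentized range exceeds 3.65/√R (3.65 is the 5% point for four means, 380 df).

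| L | R | Single-contrast error | Family error, formula | Family error, simulation |
|---|---|---|---|---|
| 0.10 | 1.0/0.6 = 1.67 | 12.9% | 19.0% | about 19% |
| 0.25 | 1.75/0.75 = 2.33 | 19.9% | 33.1% | about 32% |
| 0.50 | 3.0/1.0 = 3.00 | 25.8% | 44.5% | about 45% |

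The simulation used 6,000 balanced data sets per setting. With the term in the model, family error was about 5%. With L = 0 and no term, it was also near 5%.

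This applies to loads averaged over feet. For two loads within one foot, the true and the reported variance are both 2(E + L)/n.

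**Step 4. Planned foot contrast within one load.** The subject-by-load effect cancels, so the true variance is 2(F + E)/n. The model reports 2[(E + 5F) + 4(E + L)]/(5n) = 2(F + E + 0.8L)/n. Ratio: 1 + 0.8L/(F + E) = 1.08, 1.20 or 1.40.

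**Step 5. Interaction test.** It has (5−1)(5−1) = 16 df. Under the null, its numerator has expectation E, while the pooled denominator has E + L. Omitting the term therefore makes this test conservative too.

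**The case against.** The load clause is one sentence in an unnumbered summary. The Objectives govern, and the within-load foot tests match the aim and H1-H5. The interaction is in both SAP models, so the mean for every foot under every load will be available. The error rates belong to contrasts nobody has planned and rest on an assumed variance; if that variance is zero, there is no inflation. New tests also widen the scope: with the SAP's five outcomes, they would be 5 interaction tests and 5 × 6 = 30 load contrasts, with no rule for which outcome defines the best load.

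Most of this stands. A reader might infer that half of the trial's question goes unanswered, or that the trial cannot say anything about carrying methods. The documents support neither: no formal hypothesis is left without a test, and load contrasts can be drawn from the same fit. What survives is that the summary clause and the load-dependence rationale have no planned test. The subject-by-load omission also matters when loads are not compared, because it bears on the planned foot contrasts (step 4).

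**Conclusion.** The point holds as an inconsistency between the protocol summary and the Objectives and analysis plan, joined to a gap in the random-effects structures considered. Its size is conditional on a subject-by-load variance that the documents do not give. Over the assumed range (10% to 50% of subject-by-foot plus residual variance, those two equal, n=20, balanced data), family error for foot-averaged load contrasts is about 19% to 45%, and the variance of planned foot contrasts is overstated by about 8% to 40%. If the percentages are taken of the residual alone, 10%, 25% and 50% give family errors of about 12%, 22% and 32%.

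A reader might infer that the planned foot tests have too many false positives for this reason. The direction is the reverse: they lose power. The planned foot inferences do not depend on the missing load contrasts, so this should be corrected but does not undermine the main comparison.

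**What to change.** Either carry the load question through or withdraw it.

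1. Add a subject-by-load random intercept to the candidate structures in both SAP models. This is worth doing even if loads are never compared.
2. Report the 16-df foot-by-load F-test for each outcome.
3. Report Tukey-adjusted contrasts among the four added loads, averaged over feet, or within foot if the interaction is clear. All four are 13.6 kg, so the mass in the normalisation of Protocol 5.6 is the same for each. A contrast with the no-load condition would not have that property.
4. Label these results secondary, because they lie outside H1-H5. State how multiplicity across outcomes is handled. The SAP is written in the past tense, so if the analysis is already done, mark them as added later.

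Otherwise, delete the load clause from the protocol summary and make no statement about load ranking or load dependence.

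The cost is a few lines of SAP text and code, with no new data. The downside is a few more tests, which the secondary label keeps apart from the hypotheses.

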2.0 Introduction

Prosthetic feet help facilitate a more natural gait by attempting to emulate the biomechanical functions normally provided by the anatomical foot and ankle such as body support, forward propulsion and balance control. Clinicians select prosthetic feet based on the patient's body weight and self-reported activity level. A heavier, and/or more active individual, is prescribed a stiffer prosthetic foot. Manufacturers offer products with a range of stiffnesses that are demarcated by as many as nine ordinal categories. Each category is intended to suit a somewhat narrow weight range, typically spanning ~10 kg (~22 lbs) at an activity level defined as low, moderate or high impact. Changes in body weight can precipitate a change in the prescribed stiffness category, but body weight changes occur slowly and needed changes are usually addressed on an annual basis.

Changes to the load applied to a prosthesis can also happen quickly, such as when an individual carries an infant, toddler or other heavy item. Infants, who are unable to mobilize independently, have a mean mass of ~6.5 kg, while toddlers, who are able to mobilize independently, exhibit a range from 11.5 to 19.7 kg [1]. Women carry children more often than men [2], but men are more likely to carry older children [3]. Children and objects can be carried in different ways [4][5], but the most common methods include posteriorly in a backpack, anteriorly in a sling or with arms, or asymmetrically with arms on either side (see Fig. 1). Carrying loads in general cause an increase in oxygen consumption [6], but loads carried posteriorly are less metabolically costly [7]. However, American children are most often carried on the front [8]. Side carrying is less common [8], but allows more accessible interaction between the child and parent [3]. While non-human primates infants use their grip to assist with carriage, human parents get little to no help from their infants [3].

Carrying loads is a frequent part of many jobs. Civilian workers spend almost 4.5 hours per workday standing or walking and the mean maximum weight lifted or carried in their jobs is about

16 kg [9]. Approximately 14% of all civilian jobs had a strength level of “heavy work”, defined as occasionally carrying 23 to 45 kg, frequently carrying 12 to 23 kg, or constantly carrying items of 4.5 to 11 kg or less [10]. Among occupations, heavy work accounted for 46% of jobs in construction and extraction, 35% of jobs in installation, maintenance, and repair, 32% of jobs in transportation and material moving, and 22% of jobs in healthcare support [10]. Fully 45% of civilian jobs had a “medium work” level, defined as occasionally carrying 10 to 23 kg, frequently carrying 5 to 11 kg, or constantly carrying items of 5 kg or less [10].

Not surprisingly, individuals with lower limb amputations respond to load carriage conditions with greater metabolic costs [11] and asymmetric biomechanical deviations such as increased intact limb joint power generation and absorption and greater dorsiflexion of their prosthetic foot in late stance [12]–[14]. As discussed in the recent work by Koehler-McNicholas [15], this greater dorsiflexion of prosthetic feet is in stark contrast to the unaltered kinematics of the ankle-foot motion in non-amputees and suggests a significant short-coming in these devices. During added load conditions, a prosthetic foot with greater stiffness would be clearly desirable [16], but this benefit would be offset in the no load condition because the energy storage and release function, which facilitates locomotion, is reduced [17].

[figure not shown]

Fig. 1: Load carriage techniques.

While the biomechanical deviations depend on load magnitude and carriage technique, the negative consequence of load carriage include injuries such as foot blisters, pain and inflammation of the foot, knee and back, and stress fractures [5]. Individuals with vulnerable limbs due to trauma or diabetic/dysvascular etiologies are hypothesized to be at even greater risk for these common injuries.

For individuals with lower limb amputations who routinely carry loads using techniques (see Fig. 1), clinicians have several low-cost options including the prescription of a stiffer category foot, the addition of a heel wedge to stiffen the heel, or the prescription of a dual keel prosthetic foot (see Fig. 2). The dual keel prosthetic foot has a full-length primary keel and a truncated secondary keel. As additional loads are applied, the primary keel engages the secondary keel such that the prosthetic foot becomes stiffer. Aside from some weighted walking tests (n=3) with the dual keel prosthesis, where a weighted vest placed the additional load near the body's center of mass such that the resulting biomechanical gait deviations were, little evidence exists to support these prescription practices.

Fig. 2: Study prosthetic feet: Vari-Flex Low Profile (Össur), Vari-Flex Low Profile with 6.8° heel-stiffening wedge (shown in blue), Thrive dual keel (Freedom Innovations).

A more expensive prescription option is a commercially available

powered ankle-foot (Empower, Otto Bock, Austin, TX). The clinical value of this device is an open question with some research suggesting a benefit (e.g., [18][19][20]) and other research suggesting mixed results (e.g., [21][22][23][24]). Efficiency (laboratory testing) and efficacy (real world testing) during load carriage has yet to be demonstrated.

The target population of this research are veterans with lower limb amputation. In 2002, 82,000 Americans had a lower limb amputation arising from complications associated with diabetes [25]. The direct U.S. hospital costs related to these procedures could be conservatively estimated to exceed \$350M annually [26]. Available data suggests the VA performs between 3,000 and 5,000 lower limb amputation surgeries on veterans of diabetic and dysvascular etiology each year [27][28]. These veterans are among the 623,000 Americans who live with a major lower limb amputation [29], a population whose growth due to diabetes doubled between 1990 and 2008, but has since fortunately plateaued [30] despite an aging and overweight population. An additional cohort of Veterans stems from the U.S. involvement in the enduring military conflicts overseas (e.g., n=1,795 major limb amputation (all causes) from 2000 to 2011 [31]; n=1,645 major limb amputation (battle injuries) from 2001 to 2015 [32]). These individuals tend to have few comorbidities and may be expected to rely on the VA for their rehabilitative care for many years to come.

This research will not specifically target vulnerable populations for enrollment.

